2-month follow-up assessment. After completion of the 8-week text message intervention, participants will be invited to complete a 2-month follow-up assessment to assess short term effects of the intervention on PBS use (or non-use), motivations for PBS use, quality of PBS use, alcohol use, CAM and SAM use, and related consequences. Participants will be invited via text message and email containing a link to this 2-month assessment. Participants will receive an email shortly before the 2-month follow-up assessment, letting them know that the assessment is approaching. The 2-month follow-up assessment will take approximately 30 minutes to complete. Participants will be paid \$30 to compensate for their time that will be loaded onto their Greenphire MasterCard. If they do not complete the 2-month follow-up survey, we will periodically send reminders via email (up to 8), text (up to 8) and phone call (up to 5). Participants will have 30 days to complete the survey.

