personalized alcohol and cannabis PBS messages ([name] et al., 2018) and reasons for using alcohol and cannabis PBS. The online intervention component will focus on increase motivation to change alcohol and cannabis use and to increase motivations to use PBS in a higher quality and more consistent manner. For example, the online intervention will seek to increase motivations to use PBS by exploring consequences that young adults might wish to avoid as a result of their alcohol and/or cannabis use and then provide suggestions on ways they can reduce consequences. Further, participants will be guided through informational modules related to the role of alcohol and cannabis as it relates to concerns with aggression, legal issues, sleep, boredom, relationship issues, finances, eating and appetite, anxiety and depression, social interaction, sexual behavior, cognitive impairments (i.e., attention, concentration, memory), work or school related issues, as well as other physical health impacts including risk of dependence. These modules will be personalized based on responses participants provide in the baseline survey so that they will only see modules pertaining to concerns that they selected. Information on other reasons that young adults may wish to reduce harms from alcohol and cannabis use will also be shared with the intention of using these topics as potential motivators for change among participants.

Participants will be asked to rate each topic in the online intervention by responding to 2 items that address how useful the information is to that participant and how much the participant enjoyed the content. Participants will then be provided specific information on how to minimize consequences they may wish to avoid by using PBS in a more consistent and quality manner for those specific topics that were most relevant to them. Thus, we can tailor remaining online intervention content directly to what is the most relevant and motivating for each individual participant.

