Our prior research shows that young adults perceive TMs with personally, self-selected alcohol PBS as more useful than PBS chosen at random or selected by researchers ([name] et al., 2018). Thus, it is beneficial to tailor PBS interventions to optimize perceived relevance and to increase motivation to use PBS and to implement PBS with high quality. As such, participants will be asked in the online program evaluation survey to choose 12 alcohol PBS and 12 cannabis PBS that they are motivated to use (from a list of possible PBS for alcohol and cannabis). Participants will also identify whether they prefer to receive that alcohol or cannabis PBS content during the week and/or on the weekend, and at what time of day they would like to receive the PBS. For each self-selected PBS, the interactive online intervention will prompt them to provide information about why they selected that particular PBS. Participants may also receive a series of interactive text messages related to the PBS text messages they receive (i.e., On a scale of 1-5, how useful did you find the strategy that you received?).

Finally, participants will receive information about the daily surveys they will be receiving for the 8-week intervention survey.

The expected length of time to complete the online intervention is 20-30 minutes.

Participants will be asked to provide brief feedback on the personalized information by responding to 2 items presented after each module that will assess how useful and enjoyable the content was.

If participants do not complete the online intervention and feedback on personalized information, we will periodically send reminders via email (up to 6), text (up to 6) and phone call (up to 5). Participants will have 30 days to complete the online intervention and feedback on personalized information.

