Feasibility and acceptability for TM content. This information is subject to change based on the feedback collected from the focus groups/cognitive interviews being conducted in Phase 1. TMs will consist of a two-way dialogue, to assess whether participants read the message, participant response after reading TMs, whether alcohol or cannabis was being used when TMs were sent/read. Adherence will be calculated by the percentage of TMs that prompted a participant response ([name] et al., 2018). Participants will respond by indicating helpfulness, likeability, thought-provoking, and clarity (e.g., 1 = not at all to 5 = very). We will track message timing, response, recall, and content of messages to determine factors that may impact intervention efficacy as well as alcohol or cannabis use. We will examine response rates to intervention TMs on days alcohol and/or cannabis use were reported.

2) **Data Analysis and Data Monitoring** - *Describe plans for statistical analysis of data when appropriate. If a data safety monitoring committee is appropriate to protect the safety and/or welfare of subjects, describe its operation (e.g., membership, stopping rules and frequency of review).*

Data Analysis and Power.

Prior to any inferential statistics, univariate and bivariate descriptive statistics will be used to examine distributions and simple associations among variables. Preliminary analyses will include nature of missing data and identification of extreme values. Baseline equivalence on PBS, alcohol, and cannabis measures and demographic representation across conditions in Phase 2 will be examined. Feasibility and acceptability will be the primary outcomes for Aim 2. Behavioral alcohol and cannabis outcomes (PBS use, PBS motivation, PBS quality, alcohol use, alcohol consequences, cannabis use, cannabis consequences, CAM use, SAM use) will provide estimates of base rates and variance in outcomes to determine power for a R01 application as this program of research transitions to a Stage II study.

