Acceptability of the intervention will also be determined by: (1) proportion of eligible young adults enrolled (80% of eligible young adults agreeing to participate); (2) young adult participants' ratings of individual intervention components including both online and text message content (rating content as favorable overall, attention-grabbing, interesting, enjoyable), (3) young adult participants' ratings of accessibility (acceptable length of intervention, acceptable timing of intervention delivery), usability (ease of viewing and navigating intervention online and via TM), convenience (mode of intervention delivery), and relevance of intervention content (engaging and helpful content, thought-provoking), and (4) the proportion of young adults who would recommend the program (outside of a paid research study). Acceptability will be achieved if 80% of responses in each domain are rated a 4 or higher (out of 5). For the System Usability Scale, scores below 4.0 on the 5-point items indicate a need to re-examine intervention features, and scores of 68 or higher of the 100-point total support overall usability. In the case that intervention areas do not meet these criteria, the investigative team will revise intervention components prior to a future large-scale randomized trial. The Website Analyses and Measurement Inventory (WAMMI) consists of 20 validated statements used to evaluate websites or intervention programs. We will use this measure to assess acceptability of our online and text message intervention. Each statement is rated on a 5-point scale from strongly agree to strongly disagree and scores are calculated for Attractiveness, Controllability, Efficiency, Helpfulness and Learnability as well as an overall global usability score. All scores are automatically calculated by the WAMMI website and compared to large international database of scores for other projects. A global usability score of 50 or higher indicates that a given website or intervention program is above average (50) for usability and accessibility according to a large international database maintained by the creators of the Website Analyses and Measurement Inventory.

H2b: We expect that receiving the intervention will be associated with short-term (2-month) increases in PBS use, motivations for PBS use, and quality of PBS use as well as decreases in motivations for PBS non-use and reductions in past 2-month alcohol use, CAM and SAM use, and related consequences.

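### H2b and H2c name alcohol use and combined use as outcomes but not cannabis use itself, although the intervention targets it and the plan lists it as a behavioural outcome

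*Combined protocol and SAP*

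**What the plan says.** All places are in the combined protocol and SAP.

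- **E.2, H2b.** Receiving the intervention is expected to raise PBS use, motivation and quality, to lower motivation for non-use, and to bring "reductions in past 2-month alcohol use, CAM and SAM use, and related consequences".
- **E.1, 2-month follow-up assessment.** The stated purpose of the survey ends with the same list: "alcohol use, CAM and SAM use, and related consequences".
- **E.2, H2c.** The event-level outcomes are alcohol use, the likelihood of concurrent (CAM) or simultaneous (SAM) use, and negative consequences.
- **E.2, Data Analysis and Power.** After three PBS outcomes, the behavioural outcomes are "alcohol use, alcohol consequences, cannabis use, cannabis consequences, CAM use, SAM use". All of them "will provide estimates of base rates and variance in outcomes to determine power for a R01 application". The same paragraph says: "Feasibility and acceptability will be the primary outcomes for Aim 2".
- **E.1, Intervention Condition.** The online component is to "increase motivation to change alcohol and cannabis use and to increase motivations to use PBS", and participants "choose 12 alcohol PBS and 12 cannabis PBS that they are motivated to use".
- **G.3, benefits.** Interventions of this kind are expected to lower use of both substances.
- **E.1, Baseline and 2-month follow-up measures.** Both surveys carry a cannabis version of the Daily Drinking Questionnaire (DDQ) that records days used and hours high.

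**The concern.** Of the nine behavioural outcomes listed in E.2, cannabis use is the only one with no counterpart in H2b. CAM and SAM cannot stand in for it. Both require alcohol as well as cannabis, so a day that moves from co-use to cannabis only leaves the CAM/SAM count whatever happens to cannabis use overall.

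At stake is how the between-arm results are read. A shift from drinking with cannabis to cannabis alone could look favourable on alcohol use and on SAM use, and on CAM use if that is scored by day. No cannabis-use outcome would be set against it. Because cannabis use has no stated direction or test under H2b, whether and how to test it could be settled after the data are seen. The plan itself allows that cannabis use may worsen, since section G provides for referral of participants with worsening trajectories. The pilot is also meant to supply preliminary effect sizes, and a cannabis-use effect is one that the next trial would need.

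**Working it through.** **1. The lists side by side**

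| Behavioural outcome (E.2) | In H2b? | In the 2-month survey purpose? |
|---|---|---|
| PBS use, motivation, quality | yes | yes |
| Alcohol use | yes | yes |
| Alcohol consequences | yes, as related consequences | yes, same wording |
| Cannabis consequences | plausibly, same phrase | plausibly |
| CAM use, SAM use | yes | yes |
| Cannabis use | **no** | **no** |

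The H2b model paragraph mentions days high, but only as an example of a non-normal count outcome. In the H2c/H2d paragraph, daily cannabis use appears as a covariate.

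**2. What the named outcomes can and cannot see**

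Let A be alcohol-only days, M cannabis-only days, and CAM and SAM the two kinds of co-use day.

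- Alcohol days = A + CAM + SAM
- Cannabis days = M + CAM + SAM

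M enters only the second line. No day-count use outcome named in H2b depends on it.

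**3. Illustration (all day counts over 2 months are assumed; the documents give none)**

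| | A | M | CAM | SAM | Alcohol days | Cannabis days |
|---|---|---|---|---|---|---|
| Control | 6 | 10 | 4 | 6 | 6+4+6 = 16 | 10+4+6 = 20 |
| Intervention | 8 | 16 | 3 | 3 | 8+3+3 = 14 | 16+3+3 = 22 |

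Alcohol days, CAM and SAM all move as H2b predicts, while cannabis days rise by 2. Now hold A, CAM and SAM at the intervention values and vary M:

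- M = 10: cannabis days 10+6 = 16, a fall of 4 against control.
- M = 14: 14+6 = 20, no difference.
- M = 16: 16+6 = 22, a rise of 2.

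The named use outcomes are identical in all three cases. H2b as worded cannot tell a benefit on cannabis use from no effect or an increase.

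**4. A limit on step 3**

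The counts treat CAM as a number of days. In the surveys that H2b uses, CAM is derived from reporting both substances within the same timeframe. If that timeframe is the recall period, a participant who still uses both at all stays CAM-positive, and CAM would not improve. The step then holds for alcohol days and SAM only.

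**5. Is the outcome available, and is the sample adequate?**

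Inclusion requires cannabis use on at least 3 days in the past month, so all 240 participants have the outcome at baseline. The plan gives no alpha, power or effect size for H2b, so there is no figure to reproduce. For context, assume two-sided alpha 0.05, 80% power and a simple two-arm comparison in SD units:

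- Detectable difference = (1.960 + 0.842) × √(2/n)
- n = 120 per arm: 2.802 × 0.1291 = 0.36 SD
- n = 108 per arm (90% retention): 2.802 × 0.1361 = 0.38 SD
- Power at 120 per arm is 34%, 64%, 87% and 97% for 0.2, 0.3, 0.4 and 0.5 SD.

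Naming cannabis use needs no new data. A small effect would have to be read from the estimate and its interval rather than from the test.

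**The case against.** The strongest reply is that most of the cannabis side is already covered. H2b's related consequences can be read to include cannabis consequences, which both surveys measure and which H2d spells out for both substances. H2b's PBS outcomes are not confined to alcohol, so the 12 cannabis strategies do have outcomes, and these are the intervention's proximal targets. The days-high example suggests that a cannabis model was intended. The base-rate sentence applies to every behavioural outcome and does not single out cannabis use. No decision rule hangs on H2b, and a pilot need not predict change in every variable that it measures.

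Most of this stands, and it rules out several stronger inferences that a reader might draw:

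- **That a harmful cannabis effect would not count against H2b at all.** A rise in cannabis consequences would count, on the natural reading.
- **That the cannabis half of the strategy content goes unevaluated.** Cannabis PBS use, motivation and quality fall within H2b's wording.
- **That substitution would look like success on every use outcome.** This depends on how CAM is scored.
- **That the plan rules out a cannabis-use analysis.** It collects the data and lists the outcome. What is incomplete is the hypothesis.

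The reply does not close the gap in use itself. Consequences are not use, and an example of a count outcome is not a named outcome with a direction and a test.

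**Conclusion.** The concern holds in a limited form. H2b, the 2-month survey purpose and H2c leave out cannabis quantity and frequency, although the plan lists cannabis use as an outcome, targets it and measures it at both time points. What goes unseen is chiefly cannabis-only days and hours high. A move from co-use to cannabis-only use could read as favourable on alcohol and SAM use, and on CAM use if scored by day, with nothing to offset it.

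The omission follows from the text alone, and the possibility of masking follows from the definitions of CAM and SAM. The size of any masking rests on assumed day counts and cannot be estimated from the documents. The effect is confined to the interpretation of secondary pilot outcomes and to the effect sizes taken into the next trial. The primary conclusions on feasibility and acceptability are untouched. It should be corrected, but it does not threaten the study.

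**What to change.** 1. Add cannabis use to the H2b outcomes and to the stated purpose of the 2-month survey: days used and hours high from the parallel DDQ, analysed with the same condition-by-time GLMM.
2. State in H2b that related consequences means both alcohol and cannabis consequences.
3. State whether survey CAM is scored by day or over the recall period.
4. If cannabis use is also made an H2c outcome, drop same-day cannabis use from that model's covariates. The H2c/H2d paragraph now puts it in all analyses. Daily alcohol use is in the same list, so the H2c models with alcohol use as outcome need the same exception.
5. State whether the Benjamini-Hochberg adjustment covers H2b. It is written in the H2c/H2d paragraph, and no H2b family is defined. If it does cover H2b, include the new tests.

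**Cost.** No new data and no larger sample. There are one or two more H2b models, a slightly larger set of tests, and a revised covariate set if H2c is extended.

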H2d: We will examine whether days when young adults use alcohol alone, compared to both CAM and SAM use days, are associated with greater use of alcohol PBS, greater motivation to use alcohol PBS, less motivation for non-use of alcohol PBS, and higher quality of alcohol PBS use. Similarly, we will examine event-level associations between PBS use and consequences (alcohol and marijuana) to determine whether PBS are as effective at reducing consequences when CAM or SAM use occurs.

H2c and H2d utilize event-level data and can be tested with GLMM, which is also used for H2b. The 2-level model accounts for the clustering of observations whereby daily surveys (Level 1: day-level) are nested within individuals (Level 2: person-level). GLMM can accommodate unequal observations per person. We will employ an appropriate modeling distribution for all outcomes (e.g., zero-inflated Poisson distribution for count outcomes like consequences; normal distribution for PBS motivation). We will evaluate whether model assumptions are met (e.g., normality of error terms) so that data are modeled appropriately (Atkins & Gallop, 2007). Centering of predictors and controlling for the associated higher-level effects will be done based on standard practice and current recommendations. Biological sex and age will be person-level covariates in all analyses, and daily-level covariates will be alcohol use, cannabis use, weekend, and readiness to change in all analyses. We will also consider adding daily-level covariates related to the COVID-19 pandemic if deemed necessary. Due to the large number of models, p-values will be adjusted (Benjamini & Hochberg, 1995).

Event-level designs using daily surveys produce rich and complex data sets that permit the examination of different types of associations among constructs, and these complex associations can be tested with GLMM. For instance, H2c specifies that on days when individuals' motivations to use PBS are elevated (i.e., higher than their own average level), they will report lower alcohol use. Here, PBS motivations is the predictor (person-centered) and number of drinks consumed that day is the outcome. A cross-level interaction between the predictor (Level 1) and condition (Level 2) can be tested to determine whether this effect is stronger among those in the intervention condition compared to the assessment-only control condition. GLMM specifications can easily be modified for the event-level data to test all the hypotheses specified by H2c and H2d. For instance in H2d, each day will be coded as: neither alcohol nor marijuana, alcohol alone, marijuana alone, CAM, or SAM. Then dummy codes will be created to make specific comparisons (e.g., alcohol alone days versus SAM use days).

3) *Data Storage and Confidentiality* – *Describe where the research data will be stored during the study and how it will be secured. The investigator must take necessary steps to maintain confidentiality of data. This*

includes coding data and choosing an appropriate and secure data storage mechanism which will prevent unauthorized access to data. State who will have access to the data. If data with subject identifiers will be released, specify the person (s) or agency to whom the information will be released and the purpose of the release. For specific language, please refer to the NTR IRB's [Data Storage and Security Guidance](#) document.

Screening, Baseline, Feedback, and 2-month follow-up Data. Survey data will be identified only by a seven-digit PIN (personalized identification number) randomly generated for research purposes, and will not be identified by participants' names. Participants are assigned a PIN at the start of the online screening survey. This PIN will be embedded in all communications in which a link to surveys is sent. The PIN embedded in the survey link means that the link is specific to that individual and their survey data will be connected to that PIN. Thus, participants will not ever need to enter their PIN for purposes to complete study surveys. Participants are further protected by having an embedded PIN. An embedded PIN is more secure than emailing the PIN to participants as participants do not have to worry about keeping this information private. There is also less participant burden with the use of an embedded PIN as emailing the non-embedded PIN would require doing so in a separate communication than the survey link. The participant's PIN is kept separate from their personal information, so that without their PIN, none of their answers can be linked to anything that might identify them. Only the researchers will know the PIN. Participants will not be identified in any research reports, data sharing/online research, databases, or presentations of the research. Their name and contact information will be accessible only to research staff for the purposes of contacting them to complete the study, and will be stored separately from their data on computers with password protection and in locked file cabinets. Screening, baseline, feedback, and 2-month follow-up surveys will be completed online via Rivulent Web Design, Inc., which provides the highest available level of protection for their confidentiality. The survey data will be retained indefinitely and will be identified only by the PIN. The master list of identifiable data (with the exception of those consenting to the re-contact provision) from screening forms will be destroyed by the end of the study for all participants. Identifiable data that will be kept separate and destroyed by the end of the study includes name, contact information, city, state, and zip code of residency, with the exception of those consenting to the re-contact provision. To determine levels of socioeconomic disadvantage using the Area Deprivation Index, we will utilize the United States Census Bureau Geocoder. This tool uses unique ID numbers to link participants' addresses provided at screening with their corresponding geocodes and block codes maintaining data confidentiality. Screening, baseline, and 2-month follow-up survey data will be collected via Rivulent Web Design, Inc. and be saved on a dedicated Rivulent Web Design, Inc. server for STARR lab (Drs. [name] and [name]) projects. Project EQUIP data will also be saved by the research team on LabArchives. Rivulent Web Design, Inc. and LabArchives are both HIPAA compliant. Rivulent Web Design, Inc. and LabArchives data are encrypted, password protected, and HIPAA compliant. To maintain the confidentiality of data submitted over the internet, participants will log in to a secure website using their unique PIN created for study purposes. Data transfer will be protected using Transport Layer Security (TLS) version 1.2 or higher. The TLS encrypted session will ensure that data moving from the participant to the server (i.e., participant responses) will be encrypted in transit using a 2048-bit minimum encryption key. Data downloaded from the dedicated Rivulent Web Design, Inc. server will be stored by the research team with secure storage within LabArchives network, and is located in a locally managed datacenter. The datacenter is protected by two-step verification, configured sharing permissions, monitoring of activity, disabled permanent deletions, and conduction of regular access reviews.

EMA/Daily Data. EMA survey data will be collected via Rivulent Web Design, Inc. and be saved on a dedicated Rivulent Web Design, Inc. server for STARR lab (Drs. [name] and [name]) projects. Project EQUIP data will also be saved by the research team on LabArchives. Rivulent Web Design, Inc. and LabArchives are both HIPAA compliant. Rivulent Web Design, Inc. and LabArchives data is encrypted, password protected, and HIPAA compliant. To maintain the confidentiality of data submitted over the internet, participants will log in to a secure website using their unique PIN created for study purposes. Data transfer will be protected using Transport Layer Security (TLS) version 1.2 or higher. The TLS encrypted session will ensure that data moving from the participant to the server (i.e., participant responses) will be encrypted in transit using a 2048-bit minimum encryption key. Data downloaded from

the dedicated Rivulent Web Design, Inc. server will be stored by the research team with secure storage within LabArchives network, and is located in a locally managed datacenter. The datacenter is protected by two-step verification, configured sharing permissions, monitoring of activity, disabled permanent deletions, and conduction of regular access reviews. The EMA data/study information is immediately sent to the secure, HIPAA compliant server via the internet. All survey links have security features to keep all data confidential. This data security information has been added to all consent forms.

If a participant agrees to be contacted for future research opportunities, their personal contact/demographic information will be stored on our secure LabArchives network which is protected by two-step verification, configured sharing permissions, monitoring of activity, disabled permanent deletions, and conduction of regular access reviews. Personal contact/demographic information will only be retained for participants who give permission to be contacted for future research opportunities. This information will be kept separate from the raw research data and will only be used to inform consenting participants of future research opportunities. The master list which connects identifiers to research data will be destroyed at the close of the study, preventing any connection between the future contact information and the raw research data. In order to monitor enrollment and prevent participants from enrolling multiple times, we will keep contact information for all participants until the end of the study (or indefinitely for those who agree to be contacted for future/additional research opportunities).

In addition to the above-described data safeguards, all members of the research team have received or will receive training that includes emphasis upon the importance of confidentiality of information, and all personnel on the project (including research assistants and study staff) will complete the required NIH training in protection of human research participants. All staff will sign confidentiality statements. In addition, we have been automatically issued a federal Certificate of Confidentiality through the Department of Health and Human Services. This certificate offers the highest protection available by law for research data. We previously used these certificates in our work with high school students, college student gamblers, drinkers, cannabis users, and those who engage in risky sexual behavior. Participants will be informed of these risks and protections in the informed consent process. All recruitment contacts will emphasize the voluntary nature of participation, to reduce risks of experienced coercion. Finally, participants will be notified of the potential risk that the information provided may not be helpful, and will be provided with information about where else they might seek information about alcohol or drug use, or receive alcohol and drug-related services if desired.

4) Setting - *Describe briefly where the study will be conducted (e.g., private outpatient clinics, physicians' offices, etc.).*

The entire study will be conducted online.

Data collection will only occur at the University of North Texas Health Science Center. The University of Washington will not be a site for data collection. Participant data and safety monitoring plan, data analyses, and manuscript preparation will occur at the University of Washington.

We will comply with the NIH policy on the use of IRB for Multi-Site Research. The University of North Texas Health Science Center will serve as the IRB of record. The University of Washington will agree to rely on the University of North Texas Health Science Center to serve as the IRB of record. If any additional sites are added after the award, these sites will rely on the University of North Texas Health Science Center as the IRB of record.

The University of Washington determined this study to be "human research not engaged" and that review and approval by the University of Washington IRB was not required. Please see new document (University of Washington IRB determination).

5) Laboratory methods and facilities - *Indicate where specific laboratory tests will be performed (e.g., hospital chemistry laboratory, investigators' laboratory, radiology clinic, etc.). If None, state "N/A".*

N/A

6) Estimated Period of Time to Complete the Study – *Describe the stages and total time of subject participation as well as overall time for the entire study (start to completion). Also, if the study involves more than one visit, describe time range estimates for each visit (e.g., 20-30 minutes; 2 – 3 hours, etc.). Where possible, use a table or “bullet-point” format to clearly illustrate the flow of activities and procedures.*

- Start to finish: Approximately 8 weeks
- Online screening survey: 5-10 minutes
- Online Training Session: 30 minutes
- Online baseline survey: 30 minutes
- Online intervention (intervention condition only): 20-30 minutes
- Feedback on personalized information (intervention condition only): 10-15 minutes
- Daily surveys: 9-10 minutes each (24 surveys total)
- Online 2-month follow-up survey: 30 minutes

F. Human Subjects - *Describe the characteristics of the research population:*

1) Sample Size: *Specify the approximate number of subjects to be enrolled in this study at this site.*

Approximately 240 (120 intervention group participants; 120 assessment-only control participants) subjects at 1 sites in the U.S. will be enrolled/randomized in the study overall.

2) Describe both Inclusion AND Exclusion Criteria. *BE SPECIFIC! Include physical, mental, cognitive, medical, and other relevant Inclusion and Exclusion criteria.*

- 1) Provide first and last name
- 2) Age 18-24
- 3) Live in Texas
- 4) Valid email address
- 5) Valid cell phone number
- 6) Own a cell phone with text messaging capabilities
- 7) Have a schedule that allows for daily surveys
- 8) Have a device that supports Zoom system requirements to participate in online training session
- 9) Willing to receive study notifications and messages

- 9) Typically drink at least 3 days in the past month
- 10) Typically use cannabis at least 3 days in the past month
- 11) Report having at least 1 alcohol-related or 1 cannabis-related consequence in the past month
- 12) Report being in contemplation or action stage based on readiness to change scale for alcohol or cannabis (i.e., not in precontemplation stage)
- 13) If female, not pregnant or trying to become pregnant
- 14) Not currently in treatment for alcohol or substance use
- 15) Willing to participate in online/text message based intervention
- 16) Not having participated in a Phase 1 focus group or cognitive interview
- 17) Must correctly answer attention check questions (i.e., select 2 for "what is 4 minus 2?")
- 18) Be willing to participate in a 30-minute online training session via Zoom Video Communications
- 19) Owns a valid photo ID to present in online training session

The initial screening is conducted online to determine eligibility. Eligibility questions will be embedded in demographic and behavioral questions so as to not make criteria obvious. Rolling recruitment will be used for the proposed study. We will track participants' personal information (home address, phone numbers, date of birth) to ensure that individuals do not participate multiple times. Upon completion of screening and verification procedures, eligible participants will be sent an email with a link to the baseline survey with an embedded PIN unique to that participant. Aim 1 participants cannot participate in Aim 2.

Exclusion criteria include not meeting inclusion criteria, unwillingness to participate, failure to provide consent (e.g., declining participation in the study), providing inconsistent responses (e.g., age) identified by the survey, and having already participated in the study as identified by overlap or consistency in email addresses, contact information, and demographics. There are no other inclusion or exclusion criteria for the longitudinal portion of Aim 2 other than participants being excluded if they report that they are no longer interested in continuing their participation.

This proposal includes age-appropriate inclusion of individuals across the lifespan (ages 18-24) as this specific age range provides the best sample to address study aims. Alcohol and cannabis use are prevalent and problematic in this age range and thus age-appropriate inclusion is warranted and preferable. All participants will be 18 or older and thus are not considered children by NIH definition.

- 3) *Describe intended gender, age range, intended racial and ethnic distribution. If any vulnerable subjects are involved in this study (e.g., those with limited autonomy or decision-making capabilities), a justification must be provided.*

We will stratify recruitment based on biological sex and alcohol and cannabis use, aiming to recruit equal numbers of participants in each of the categories and targeting equal numbers of males and females in each group. We will recruit all minority participants to be above local census estimates. For the randomization to conditions (intervention or assessment-only control) we will use a stratified, blocked randomization procedure, where assignment will be balanced across biological sex and alcohol and cannabis use (Hedden et al., 2006). We will stratify recruitment based on biological sex, alcohol and cannabis use to aim for equal numbers of males and females at each group.

4) Identify the source(s) from which you will obtain your study population.

Participants will be selected by targeted online (Facebook/Instagram/Twitter; Craigslist and online newspapers) advertisements as well as in-person recruitment approaches (i.e., leaving flyers at local businesses, etc.)

5) Describe plans for recruitment of subjects. All materials (e.g., flyers, ads, emails, letters, postings, handouts, social media language, website link, etc.) that will be used for recruiting subjects must be submitted to the IRB for review. For specific guidance, please refer to the [NTR IRB Recruitment Guidance](#) document.

We will utilize multiple recruitment methods to reach a variety of participants ages 18-24 from Texas. Our experience has demonstrated success in recruiting participants using the proposed methods. Online ads will be placed in media outlets. In-person recruitment may consist of tabling at local sites and study staff handing out study flyers and study information businesses. Flyers advertising recruitment for a research study of 18-24 year olds will include information about the study and links to the study website, email address, and phone number. Website links and QR codes provided to individuals (in flyers and online recruitment ads) will lead them to the consent/assent forms. Online, print, and bus ads may be placed in local media outlets and city buses. Community organizations may be contacted via email requesting them to share the study's information with individuals in their organization. Social media outreach will consist of a Facebook Fan page that will provide a brief study description and links to the study website. We will use Facebook's advertising platform to also show our ads on Instagram. The Facebook Fan page is open to the public. Liking the Fan page is not an indicator of study enrollment. The communication for the Fan page is a one-way communication platform whereby communication will come from the study staff via Facebook. Individuals will not be able to post or comment within the Fan page. They can share posts from the page on their newsfeed. We ask participants to like or share our Fan page, but we do not ask them to post anything on the Fan page. Additionally, we created Twitter and Instagram accounts. We will use paid Facebook, Twitter, and Instagram sponsored ads, stories, and promoted boosts on our Fan page/Twitter/Instagram accounts to increase our online presence. We will also advertise in local online versions of newspapers and in high school newspapers. Online (e.g., Craigslist, Facebook, Twitter, Instagram, newspaper) recruitment ads will provide a hyper-linked website address for more information and eligibility screening. Print advertisements in local newspapers will contain a brief description of the study and various methods of contact for the study (website, phone number, email).

